10.2. Secondary Efficacy Analyses

- 1) The difference between baseline and week 12 of the proportion of time spent moving during the night will be compared across intervention groups using a t-test. The average of the first three nights of evaluable data at week 0, and the last three nights at week 12 will be used.
- 2) The proportion of children who report a reasonable (≤20%), good (>20% and ≤50%) or excellent (>50%) improvement in SASSAD score at 12 weeks, will be compared using a chi-squared test.
- 3) Amount of topical corticosteroid / calcineurin inhibitors used during the 12 week study period. This will be captured by weighing the medication at each visit. This will then be summarised by the nurses at week 12, including a measure of the degree of accuracy of any estimates. These will be spilt into two groups, low strength consisting of mild and moderate topical steroids, and high strength consisting of potent and very potent topical steroids and mild and moderate calcineurin inhibitors. The difference in the amount (in grams) of each of the two groups will be assessed using t-tests.
- 4) The difference in the change from baseline to week 4 and baseline to week 12 Patient Oriented Eczema Measure (POEM) scores will be compared using t-tests.
- 5) Difference in the number of well controlled weeks (WCW) as defined in section 8.3, will be analysed using a t-test. The number of totally controlled weeks (which are a subset of the WCW), will also be summarised.
- 6) Difference in the mean change from baseline in the Dermatitis Family Impact (DFI) questionnaire at 12 weeks, will be analysed using a t-test.

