6.2 Secondary outcomes

1. Difference between the groups in the proportion of time spent moving during the night². Movement will be captured for periods of one week at week 1 and week 12, and will be measured using accelerometers (ActiwatchTM). These units are worn by the child in the same way as a wrist watch

² This outcome has been included as an objective surrogate for sleep loss and itchiness (two of the defining features of eczema). Previous research has suggested that this is a suitable objective tool for assessing itch ^{6,7} and further pilot work is currently underway to assess its suitability for use within this trial (results available Dec 2006)

This outcome has been included as an objective surrogate for sleep loss and itchiness (two of the defining features of eczema). Previous research has suggested that this is a suitable objective tool for assessing itch ^{6,7} and further pilot work is currently underway to assess its suitability for use within this trial (results available in 2007).

- 2. Difference in proportion of children who report either good or excellent improvement in eczema severity at 12 weeks (using a 5-point Likert scale).
- 3. Difference in the amount of topical corticosteroid / calcineurin inhibitors used during the 12 week study period.
- 4. Difference in Patient Oriented Eczema Measure (POEM ⁸) collected at baseline, weeks 4, 12 and 16. This scale is a well validated tool that has been developed to capture symptoms of importance to patients (rather than objective signs that are used in traditional severity scales, such as SASSAD).
- 5. Difference in the number of totally controlled weeks (TCW) and well controlled weeks (WCW) based on the number of days with eczema symptoms and the number of days that topical treatment is applied. This outcome is based on a recent systematic review conducted by the applicants looking at ways of assessing long-term control for chronic conditions such as atopic eczema, asthma and rheumatoid arthritis ⁹. The terms TCW and WCW have been adopted for use by researchers in the field of asthma and appear to be a useful and intuitive means of capturing disease activity over time.
- 6. Difference in the mean change in the Dermatitis Family Impact (DFI) questionnaire at 12 weeks ¹⁰. This scale was chosen as an appropriate quality of life scale for the study for two reasons:

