10.4 Secondary analyses

- ♦ The proportion of time spent moving during the night will be compared using Student's t-test.
- ♦ The proportion of participants reporting either good or excellent improvement in disease severity on the global assessment scale will be analysed using a chi-squared analysis.
- ♦ A Student's t-test will be used to assess the difference in the number of grams of topical treatment applied.
- ♦ POEM scores will be compared at 12 weeks using Student's t-test.
- A Student's t-test will be used to assess differences in the number of Totally Controlled Weeks and Well Controlled Weeks throughout the study period.

- ♦ Mean scores on the Dermatitis Family Impact Scale and Quality of Life scores will be compared using a Student's t-test.
- ♦ Predictors of response model. Factors to be included in the model will be prespecified prior to analysis, but will include baseline eczema severity, previous treatment history, water hardness at baseline, prior belief relating to the benefits of softened water, demographic variables and filaggrin status (*see* Section 12).

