11. COST-EFFECTIVENESS ANALYSIS

11.1 Objective:

• To assess the cost-effectiveness of installing a water softening unit in the homes of families who have a child with eczema, when compared with usual care.

The cost analysis will compare the overall costs for the intervention to usual care, measuring resource use such as primary care contacts, medication prescribed, secondary care contacts and patient costs. Health and family resource use data will be measured using participant diaries. Resource use will be valued using published unit costs (e.g. Curtis and Netten ¹⁶, BNF 2005, and NHS reference costs (http://www.dh.gov.uk/PolicyAndGuidance/OrganisationPolicy/FinanceAndPlanning/NHSReferenceCosts/fs/en)), and patient reported estimates. The costs to the NHS and patient will be reported separately as well as in combination.

The primary measures of effectiveness for cost analyses purposes will be the number of participants who show a \geq 50% improvement in SASSAD at 12 weeks compared to baseline. Secondary analyses will be conducted using continuous data from the SASSAD scale; the Dermatitis Family Impact Scale; and the generic measure of health utility as measured on the child version of the EQ-5D (for children aged 3–6 years, the proxy version will be used).

If non-dominance occurs an incremental cost-effectiveness ratio will be produced. Sensitivity analysis will be undertaken to test the robustness of results in the face of any uncertainties or assumptions made in the analysis. In particular, assumptions about the time period over which the difference in costs and difference in benefits are likely to be sustained. Where appropriate the change in health-related quality of life measured on the

EQ-5D will be multiplied by the expected duration of benefits from water softening in order to calculate the Quality Adjusted Life Years (QALYs) of the intervention group compared to the usual care group.

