3.2. Secondary Endpoints

- 1. The difference between baseline and week 12 of the proportion of time spent moving during the night. Movement will be captured for periods of one week at weeks 1 and 12, and will be measured using accelerometers (Actiwatch). These units are worn by the child in the same way as a wrist watch. Due to possible differences between the units every effort was made to ensure the children always used the same unit and where this was not the case this has been documented. A sensitivity analysis will be performed excluding those who did not use the same unit throughout the trial.
- 2. Difference in the proportion of children who report either a good or excellent improvement in eczema severity at 12 weeks (using a 5-point Likert scale). As these data were not collected¹, responders will be grouped into three groups; those who report a reasonable (≤20%), good (>20% and ≤50%) or excellent (>50%) improvement in SASSAD score at 12 weeks.
- 3. Amount of topical corticosteroid / calcineurin inhibitors used during the 12 week study period. This information is captured by weighing the medication at each visit and then summarised according to steroid strength to give the total amount used from baseline to week 12. Nurses will also be providing an indication of the level of accuracy of any estimates. A sensitivity analysis will be performed excluding those for whom the nurse is not confident about the amount of medication used.
- 4. Difference in Patient Oriented Eczema Measure (POEM). This scale is a well validated tool that has been developed to capture symptoms of importance to patients (rather than objective signs that are used in traditional severity scales, such as SASSAD).
- 5. Difference in the number of totally controlled weeks (TCW) and well-controlled weeks (WCW) based on the number of days with eczema symptoms and the number of days that topical treatment is applied up to primary endpoint at 12 weeks. This will be derived from the symptom diaries.
- 6. Difference in the mean change from baseline in the Dermatitis Family Impact (DFI) questionnaire at 12 weeks.

-

Omitted from CRFs to avoid unblinding of research nurses, and also on reflection this measure would be too open to bias in a single-blind study. Therefore improvement based on improvement in SASSAD score is preferable.

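### SAP secondary endpoint 2 has no class for children who did not improve, so they count as reasonable improvement, and its chi-squared test ignores the order of the classes

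*Combined protocol and SAP*

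**What the plan says.** Protocol 6.2 item 2 planned a binary, self-reported endpoint: "Difference in proportion of children who report either good or excellent improvement in eczema severity at 12 weeks (using a 5-point Likert scale"). Protocol 10.4 matched it with a one-degree-of-freedom test, the proportion "reporting either good or excellent improvement in disease severity on the global assessment scale will be analysed using a chi-squared analysis".

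The Likert item was not collected. SAP 3.2 item 2 says so, explains why in a footnote ("Therefore improvement based on improvement in SASSAD score is preferable"), and substitutes this rule: "responders will be grouped into three groups; those who report a reasonable (≤20%), good (>20% and ≤50%) or excellent (>50%) improvement in SASSAD score". SAP 10.2 item 2 repeats the three classes ("The proportion of children who report a reasonable (≤20%), good (>20% and ≤50%) or excellent (>50%) improvement in SASSAD score at 12 weeks") and states that they "will be compared using a chi-squared test". It names no trend or rank version, and no effect measure or interval for this item.

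Four other places bear on the point:
- SAP 5 defines the ITT population as all randomised participants with evaluable data and treats secondary endpoints as supportive.
- SAP 10.3 item 3 defines a responder as a 20% or 50% decrease in SASSAD.
- Protocol 10.3 sets NNT cut-offs at ≥20%, ≥50% and ≥75%. SAP 10.1 keeps 20% and 50% and gives no inequality sign.
- Protocol 11.1 counts, for cost-effectiveness, children with at least a "50% improvement in SASSAD at 12 weeks compared to baseline".

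**The concern.** An improvement of 20% or less, with no lower limit, includes zero and every negative value. No other class is available for those children, so the three classes, all named as improvement, add up to 100% in each arm. A reader of the results table would take the first column to be children who got somewhat better, when under the SAP's own planning figures most of them did not.

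The test also no longer fits the endpoint. SAP 3.2 still opens with the proportion reaching good or excellent, which is a binary comparison. SAP 10.2 tests a table with two arms and three ordered classes. An ordinary chi-squared statistic on that table is the same whichever way the columns are arranged, so it cannot use the fact that excellent is better than good and good better than reasonable. At stake are the readability of one secondary result and some of its power.

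**Working it through.** **Inputs.** From SAP 4: mean baseline 20, SD of change 10, difference 20% of 20 = 4 points, 5% significance (taken as two-sided), 90% power, 15% attrition. Assumed, because the documents do not give it: control mean improvement μ of 0, 2, 4 or 6 points, with normally distributed change.

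**The plan's own figure.** n per arm = 2 × [10 × (1.960 + 1.282) / 4]² = 131.3, so 132. Then 264 / 0.85 = 310.6, which agrees with 310. The checks below use 132 evaluable children per arm.

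**Who is in the lowest class.** With baseline 20, the 20% cut is 4 points and the 50% cut is 10 points. For an arm with mean improvement μ:
- share in the lowest class = Φ((4 − μ)/10)
- share unchanged or worse = Φ((0 − μ)/10)

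The immediate arm has mean μ + 4.

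| Control μ | Delayed: ≤20% | Delayed: unchanged or worse | Fraction of class | Immediate: ≤20% | Immediate: unchanged or worse | Fraction of class |
|---|---|---|---|---|---|---|
| 0 | 65.5% | 50.0% | 76% | 50.0% | 34.5% | 69% |
| 2 | 57.9% | 42.1% | 73% | 42.1% | 27.4% | 65% |
| 4 | 50.0% | 34.5% | 69% | 34.5% | 21.2% | 61% |
| 6 | 42.1% | 27.4% | 65% | 27.4% | 15.9% | 58% |

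A simulation with whole-number scores and varying baselines (minimum 10, mean 20, shape assumed) gave 68% to 79% of the class in the delayed arm and 61% to 72% in the immediate arm.

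**Reading the rule as improvers only.** At μ = 2 the table would keep 132 × (1 − 0.421) = 76 delayed and 132 × (1 − 0.274) = 96 immediate children. Good or excellent would be 0.421/0.579 = 72.6% against 0.579/0.726 = 79.8%, a difference of 7.2 points. Among all children it is 57.9% − 42.1%, about 16 points. The two readings therefore give different results, and the second selects on the outcome.

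**Power of the test.** Write p₀ⱼ and p₁ⱼ for the class shares in the delayed and immediate arms.
- Unordered, 2 df: λ = 132 × Σ(p₀ⱼ − p₁ⱼ)²/(p₀ⱼ + p₁ⱼ). At μ = 2 the shares are 0.579, 0.209, 0.212 and 0.421, 0.235, 0.345. So λ = 132 × (0.0252 + 0.0015 + 0.0316) = 7.69 and power is 70%.
- Trend, 1 df, scores 0, 1, 2: λ = 132 × d²/(2v), where d is the difference in mean score and v the pooled variance. At μ = 2, d = 0.291 and v = 0.729, so λ = 7.68 and power is 79%.

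The noncentrality is almost the same. The trend test gains because it spends one degree of freedom instead of two.

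| Control μ | Chi-squared, 3 classes | Trend, 3 classes | Binary >20% | Trend, 4 classes |
|---|---|---|---|---|
| 0 | 68% | 77% | 73% | 82% |
| 2 | 70% | 79% | 73% | 83% |
| 4 | 71% | 80% | 73% | 83% |
| 6 | 71% | 80% | 71% | 82% |

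The fourth class is no change or worse. With varying baselines, simulated power for the first three columns was 66% to 70%, 76% to 79% and 69% to 74%.

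**The case against.** The strongest reply is that little depends on this. SAP 5 rests inference on the primary t-test and calls secondary endpoints supportive. The same SASSAD scores are already tested on the continuous scale with about 90% power. The chi-squared test keeps its type I error, and no power is claimed for this item. The NNTs in SAP 10.1 already rest on differences in responder proportions, so a risk difference largely repeats planned output. All of that stands, and it limits the weight of the point.

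A reader might infer that improvement rates are inflated in both arms. The documents do not support that. The quantity SAP 3.2 names is good or excellent, above 20%, and non-improvers fall correctly below that cut. No overall rate of any improvement is planned. The fault lies in the name and contents of the bottom class.

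A reader might also infer a wide conflict over cut-offs. Protocol 11.1 has a 50% cut-off only; ≥20% appears for the NNT in protocol 10.3. Exact falls of 20% and 50% are rare: about 1% and 1% to 2% of children in simulations with assumed baseline shapes. A child going from 20 to 10 does count as a success in the economic analysis but not as excellent here, which is worth tidying and no more.

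Nor is the substitution hidden, since SAP 3.2 discloses it with reasons.

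The reply does not remove the missing floor. The word responders in SAP 3.2 cannot supply one: restricting to improvers conflicts with SAP 5, and the responder definition in SAP 10.3 does not fit a class of 20% or less.

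**Conclusion.** The point holds as a specification fault in one supportive endpoint. As written, unchanged and worsened children are reported as reasonable improvement, and they make up about 58% to 76% of that class across the two arms. The chi-squared test is valid but gives up about 9 points of power against a trend test on the same table.

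These sizes rest on the SAP's baseline, SD and 4-point effect, on normal change scores, and on an assumed control mean improvement of 0 to 6 points. The missing floor and the order-blind test follow from the text alone. The good and excellent proportions, the primary analysis, the NNTs and the sample size are unaffected.

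**What to change.** In SAP 3.2 item 2 and 10.2 item 2:
1. Define percentage change explicitly and use four ordered classes, the lowest being no change or worse.
2. Replace the ordinary chi-squared test with an ordered one, either a trend test or a proportional-odds model.
3. Report the difference between arms in the good-or-excellent proportion with a 95% confidence interval.
4. As tidying, set the inequalities to match the NNT cut-offs (≥20% and ≥50%, protocol 10.3) and the cost-effectiveness cut-off (≥50%, protocol 11.1). The classes become ≤0%, >0% to <20%, 20% to <50%, and ≥50%.
5. Delete the wording that children report the result, since protocol 6.1 has the nurse score SASSAD without participant input.

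The cost is small: SAP wording and analysis code for a supportive endpoint, with no new data. The changes should be made before the allocation codes are revealed. The trade-off is that an ordered test is less sensitive to a non-monotone difference, for example one where softened water moved children out of the middle classes in both directions.

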7.1 Inclusion criteria

- Children aged 6 months to 16 years at baseline, with eczema as defined by the UK refinement of the Hanifin and Rajka diagnostic criteria ¹⁴.
- Eczema present at time of assessment (minimum SASSAD score of 10).
- Baseline water hardness of >200 mg/L of calcium carbonate.
- Home suitable for the installation of a water softening device (as assessed by water engineer)

Only one child will be enrolled per family. The choice as to which child becomes involved will be made by the parents and children involved, taking into account the inclusion criteria above.

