10.3 Primary analyses

♦ Change in disease severity (SASSAD) at 12 weeks compared to baseline, will be assessed using Student's t-test. An adjusted analysis will also be conducted including the stratification variables of eczema severity, age and recruiting centre.

In order to aid the clinical interpretation of these data, the number needed to treat (NNT) assuming a range of improvements in SASSAD scores will also be presented ($\geq 20\%$, $\geq 50\%$ and $\geq 75\%$ improvement).

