5. ITT ANALYSIS AND MULTIPLICITY

The SWET trial will be analysed as intent-to-treat (ITT) at week 12.

The ITT population will consist of all randomised participants with evaluable data. This will be the primary population used for the main analysis, which will use the randomised treatment allocation rather than actual treatment received. An additional sensitivity analysis will be performed excluding outliers.

Primary inference will be based on the primary endpoint analysis of the ITT population. Significance will be at the 5% level.

A secondary, per protocol analysis of the primary endpoint will be performed excluding the following participants:

- Those who were randomised into the study, but who failed to receive their allocated treatment.
- Those who are deemed to be major protocol violators as determined by the Protocol Violators Group (including independent members) review of the protocol deviation log.

Criteria for protocol violators are as follows:

- Missing SASSAD score at week 12
- Group A: exposed to fully softened water for <75% of the time their home has an active water softener in place (i.e. sleeping at home + unit fully working for <75% of the time their home has an installation)

- Group A: Participant away from home or with partially functioning water softener of >2 days/week for each of the 4 weeks prior to the primary outcome measure
- Group B: Participant away from home for > 2 days/week for each of the 4 weeks prior to the primary outcome measure
- Unblinding of research nurse prior to primary outcome measurement
- Starting new treatment prior to primary outcome measurement will be examined on a case-by-case basis to determine if they comprise a protocol violator.

Baseline characteristics (as described in section 6.2) will be summarised and if any major imbalance exists the analyses will be adjusted to account for this.

Analyses of all secondary endpoints and adjusted analyses will be considered supportive to the primary analysis so no adjustments for multiple comparisons will be made.

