6.2. Other covariates

In addition to the stratification variables, other covariates to be considered in a predictors of response model are:

- Age (continuous)
- Previous treatment history (see section 8.3)
- Water hardness at baseline (WHO classification, continuous).
- Sex
- Ethnicity
- Filaggrin status
- Income
- Time away from home (based on a cut off of >21 days).

In addition, the following baseline characteristics will be summarised:

Washing powder

- Fabric softener
- Bathing/showering frequency
- Swimming frequency
- Home ownership
- Allergy

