Previous treatment history will be assessed using treatment reported at enrolment. This will be grouped into low strength (mild and moderate topical steroids) and high strength (potent and very potent steroids and mild and moderate calcineurin inhibitors). Participants will be classed as a low strength user if they only use mild and moderate topical steroids, and a high strength user if the use potent or very potent topical steroids or mild or moderate calcineurin inhibitors (even if they also use mild or moderate topical steroids).

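### Grams of low- and high-strength topical treatment are compared by unadjusted t-tests, although age and entry treatment strength are recorded at baseline and would probably sharpen the comparison

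*Combined protocol and SAP*

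**What the plan says.** **Outcome.** SAP section 3.2 item 3 obtains the amount used by weighing medication at visits, "summarised according to steroid strength to give the total amount used from baseline to week 12". There is no pre-trial usage value and no scaling for the child's size.

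**Test.** SAP section 10.2 item 3 forms a low-strength group (mild and moderate steroids) and a high-strength group (potent and very potent steroids, and calcineurin inhibitors), then states: "The difference in the amount (in grams) of each of the two groups will be assessed using t-tests". Protocol section 10.4 has a single comparison: "A Student's t-test will be used to assess the difference in the number of grams of topical treatment applied". The only sensitivity analysis for this endpoint drops children whose weights the nurse does not trust.

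**Population.** Protocol section 7.1 admits "Children aged 6 months to 16 years at baseline".

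**Covariates available.** SAP section 8.3 calculates age at randomisation and defines entry strength: "Previous treatment history will be assessed using treatment reported at enrolment", classed as low or high. Section 6.2 puts both to one use: "In addition to the stratification variables, other covariates to be considered in a predictors of response model are". Under section 10.3 that model is a logistic regression for SASSAD response.

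**Adjustment elsewhere.** Protocol section 10.3, which concerns SASSAD, says: "An adjusted analysis will also be conducted including the stratification variables of eczema severity, age and recruiting centre". SAP section 5 says of baseline characteristics that "if any major imbalance exists the analyses will be adjusted to account for this". Section 9.1 adds an adjusted analysis if imbalance is substantial.

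**The concern.** SASSAD, POEM, DFI and night movement are analysed in the SAP as change from baseline, which removes part of the stable difference between children. Grams have no baseline value, so all of that difference stays in the error term.

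Two sources of it are known at entry. An adolescent has more skin to treat than an infant. A child who enters on potent steroids is likely to use high-strength grams, and one who enters on mild steroids may use none.

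Splitting by strength divides the outcome; it does not adjust for entry class. A child who does not use a class presumably contributes zero grams to it, and those zeros make entry class a stronger predictor of each outcome.

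The stake is precision. Families are not blinded, and protocol section 8.3 counts use of topical therapy among the objective secondary outcomes, so it is worth estimating well.

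**Working it through.** **1. The plan's own figure.** The only sample size calculation for the whole trial is for SASSAD: difference 20% of 20 = 4, SD 10, two-sided 5%, 90% power.

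n per arm = 2 × (1.960 + 1.282)² × 10² / 4² = 131.3, so 132 per arm and 264 in total. Allowing for 15% attrition: 264 / 0.85 = 310.6, or 311 against the stated 310. The figure is reproduced. No SD, effect size or power is given for grams.

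**2. What a covariate is worth.** If baseline covariates explain a share R² of the variance, the SE is multiplied by √(1 − R²), and the unadjusted test needs 1/(1 − R²) times the sample for the same precision. With 310 × 0.85 / 2 = 131.75 per arm, the standardised difference detectable at 80% power is (1.960 + 0.842) × √(2/131.75) = 0.345 unadjusted.

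| Assumed R² | SE ratio | Sample ratio | Detectable difference | Power if 80% unadjusted |
|---|---|---|---|---|
| 0.10 | 0.949 | 1.11 | 0.327 | 84% |
| 0.20 | 0.894 | 1.25 | 0.309 | 88% |
| 0.30 | 0.837 | 1.43 | 0.289 | 92% |

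**3. Plausible R² (assumptions).**
- Age, for total grams with every child a user: with use rising 2- to 5-fold over the age range and a within-age CV of 0.5 to 1.5, R² is about 2% to 34%.
- Entry class, for one strength group: if a share p are users at entry and nobody else uses that class, R² = p(1 − p) / [p(1 + CV²) − p²]. For p = 0.5 and CV = 1.0 this is 0.25 / (1.0 − 0.25) = 0.33. Over p = 0.3 to 0.7 and CV 0.5 to 1.5 it runs from 12% to 74%. This is an upper bound, because entry class is taken to determine use completely.

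**4. Simulation of the outcome as planned (assumptions).** 132 per arm; age uniform from 0.5 to 16 years; size rising linearly from 0.35 to 1.75; grams = size × log-normal variation × use of the class (0 or 1); a 25% reduction with the softener; non-users counted as zero. Half the children use the class at entry. Ranges run from CV 0.5 to CV 1.0.

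| Link between entry class and use | t-test | Age | Age + entry class |
|---|---|---|---|
| All entry users, plus 10% of the others | 41–26% | 46–27% | 73–34% |
| Entry users only (upper bound) | 40–22% | 43–24% | 79–33% |
| 90% of entry users, 10% of the others | 39–22% | 42–24% | 59–30% |

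Repeat runs agree to within about three percentage points. With no true effect, rejection stays at about 5% with and without adjustment.

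In the first row, age explains about 10% to 5% of the variance and entry class about 43% to 25%. Age matters less here than for total grams because the zeros dilute it.

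**The case against.** The strongest reply is that the t-test is valid under randomisation, the endpoint is supportive, no power is claimed for it, and every input above is assumed. All of that stands. It limits how much the point matters; it does not give a reason to leave known predictors out.

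Four stronger readings are tempting, and the documents do not support them.

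- **That the comparison is biased.** Allocation is randomised 1:1, so only precision is at issue.
- **That chance age imbalance is unprotected.** SAP sections 5 and 9.1 allow adjustment for it, and protocol section 8.3 stratifies by age (SAP section 6.1 omits age). What remains is that the trigger comes after the data are seen, no threshold or model is stated, and it does nothing about noise when the arms are balanced. If age was a stratification factor, the unadjusted test is also somewhat conservative.
- **That body size is the main problem, with a few large adolescents dominating.** For total grams with a five-fold size range, age explains 35% of the variance at CV 0.5 and 13% at CV 1.0, so most of the variance lies elsewhere. For the strength-specific outcomes, adjusting for age alone gains only about 1 to 5 power points.
- **That a log-scale model would recover much more.** For total grams at CV 1.0, power is about 55% raw, 71% with an unadjusted log-scale t-test and 80% with size adjustment. So (71 − 55) / (80 − 55) = 64% of that gain comes from the assumed log-normal shape. Grams of one class will also include zeros, for which the log is undefined.

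Grams are not the only evidence on treatment use either. Diaries record days of active topical treatment (protocol section 9.1.2), and stepping up enters the controlled-weeks endpoint (SAP section 8.3).

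Entry class may also predict the two outcomes unequally. SAP section 8.3 counts a child using both strengths as a high-strength user, so it may say less about low-strength grams.

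**Conclusion.** The point holds as a loss of precision in a supportive secondary endpoint. Both documents plan t-tests on raw grams, and the SAP leaves two recorded baseline predictors to a SASSAD responder model. Entry treatment class is the more important of the two.

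The size of the loss cannot be derived from the documents. Under the central assumptions (264 children, 25% reduction, half using a class at entry plus 10% of the others), adjusting for age and entry class raises power by 73 − 41 = 32 points at CV 0.5 and 34 − 26 = 8 points at CV 1.0. With looser prediction (third row of the simulation table) the gains are 59 − 39 = 20 and 30 − 22 = 8 points. They shrink further if use is more variable or entry class predicts use less well. Primary inference on SASSAD is unaffected.

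**What to change.** In SAP section 10.2 item 3, before allocation codes are revealed:

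- For each strength group's grams, make the main comparison a linear model on randomised group, age (continuous) and entry treatment class, with a robust or bootstrap 95% CI for the difference in grams.
- Use the low and high classes of SAP section 8.3 and add a stated category for children using neither, which that section does not define.
- State that a child who uses none of a class counts as zero grams for it.
- Report raw means and the t-test alongside.
- Either plan no log-scale analysis or state how zeros are handled.

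This fixes the adjustment in advance for this endpoint, so it no longer depends on a judgement about imbalance. The cost is SAP wording and code. Age and entry treatment are already recorded, so no new data are needed.
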